6.2.6 Errors in Study Vaccine Administration

Study vaccine errors (including overdose, underdose, and administration error) must be documented as protocol deviations. A brief description should be provided of the deviation, including whether the participant was symptomatic (list symptoms) or asymptomatic, and whether the event was accidental or intentional.

Dosing details should be captured on the appropriate source documents and on the eCRF.

An overdose is the accidental or intentional administration of a study vaccine in an amount higher than the dose being studied. An overdose or incorrect administration of study vaccine is not itself an AE, but it may result in an AE. If the participant receives a dose of study vaccine that exceeds protocol specifications and the participant is symptomatic, the symptom(s) should be documented as an AE (see [Section 9](#)).

Should an overdose occur, the Investigator or designee should contact the Sponsor or designee within 24 hours.

6.2.6.1 Management of Overdose

There are no known treatments for potential overdose of study vaccine. Unless there is a user error leading to failure to administer any volume of study vaccine, “catch-up” study vaccine administrations will not be performed. In case of medication errors or an overdose, it is recommended that the participant be monitored for any signs or symptoms of adverse reactions and appropriate symptomatic treatment be provided immediately.

6.3 Licensed Study Vaccines

Flucelvax® Quadrivalent (Seqirus Pty Ltd.) is a surface antigen, inactivated influenza vaccine prepared in cell cultures and indicated for active immunization of persons aged 6 months or older for the prevention of influenza disease. Each 0.5-mL dose, in sterile phosphate-buffered saline, is a suspension of a total of 60 µg hemagglutinin (HA). HA antigens are derived from the four influenza strains (A/H1N1, A/H3N2, B/Yamagata and B/Victoria lineage, 15 µg each) recommended by the World Health Organization (WHO) for quadrivalent vaccines for the respective season.

Fluad® Quadrivalent (Seqirus Pty Ltd.) is a surface antigen, inactivated adjuvanted influenza vaccine indicated for active immunization of persons aged 65 years or older for the prevention of influenza disease. An approximately 0.5-mL dose of vaccine contains nominally 15 µg of HA of each of the 2 influenza type A strains and each of the 2 influenza type B strains for a total of 60 µg of HA in the vaccine. The strain composition is that recommended by the WHO for quadrivalent vaccines for the respective season.

6.4 Measures to Minimize Bias: Randomization and Blinding

This study will be observer-blind.

CONFIDENTIAL

May not be used, divulged, published or otherwise disclosed without written consent of Arcturus Therapeutics, Inc.

After signing the informed consent form (ICF), each participant will be given a screening number according to the screening order. On Day 1, following confirmation of eligibility, a participant number will be assigned, and participants will be allocated to treatment using an interactive response technology (IRT).

Due to the visual differences between the study vaccines, the participants will be blinded before receiving the study vaccinations. An unblinded dosing team, not involved with study participant's evaluation, will prepare and administer the study vaccine doses. The study vaccine syringe will be opacified to avoid unblinding of the participant. The administration of the study vaccine will also be performed behind a closed curtain to ensure that the other blinded staff members do not become unblinded. The investigative study center personnel, as well as the sponsor personnel involved in the monitoring or conduct of the study, will be blinded to the study vaccine code.

The laboratories in charge of immunogenicity and safety testing will also be blinded so associating the sample with an assigned treatment or study visit will not be possible.

The treatment code should be broken only if the investigator/physician in charge of the participant feels that the case cannot be treated without knowing the identity of the study vaccine.

Except in cases of medical necessity, a participant's treatment should not be unblinded without the approval of the Sponsor. If unblinding should occur (by either accidental unblinding or emergency unblinding) before completion of the study, the investigator must promptly contact the Sponsor or designee and document the date and reason that the blind was broken in the source documentation and eCRF. Instructions regarding emergency unblinding will be provided to the investigator.

6.5 Vaccine Compliance

The investigator records all injections of investigational vaccine/control vaccine given to the participant.

The prescribed dosage, timing, and mode of administration may not be changed. Any departures from the intended regimen must be recorded in the eCRFs.

Administration of study vaccines will be performed at the study center by appropriately trained staff.

The clinical staff is responsible for the ongoing safety and wellbeing of the participants while they are in the study center. There is a physician on-site during normal business hours and medical advice is available by phone 24 hours a day. In addition, if necessary, the clinical staff can contact further on-call physicians or public emergencies services in the event of a serious medical event.

6.6 Treatment after the End of the Study

The Sponsor will not provide any additional care to participants after they leave the study.

CONFIDENTIAL

7 PARTICIPANT WITHDRAWAL FROM THE STUDY

7.1 Discontinuation of Study Treatment

A “withdrawal” from the study vaccine refers to any participant who does not receive the complete treatment, i.e., when no further planned dose is administered from the date of withdrawal. A participant withdrawn from the study vaccine may continue further study procedures (safety or immunogenicity) if planned in the study protocol, as deemed appropriate by the investigator.

Primary reason relative to premature discontinuation of the study vaccine/control will be documented in the eCRF:

- AE(s);
- Participant decision, not due to an AE;
- If a female participant becomes pregnant (such participants will be followed up as described in [Section 9.1.13](#) and [Appendix 1](#));
- Lost to follow-up;
- Sponsor study termination;
- The participant tests positive for SARS-CoV-2 infection prior to Day 29 visit (prior to the second vaccination);
- Other (specify).

Contraindication for second vaccination are criteria for delay of the second vaccination are described in [Section 5.3](#).

If a participant who does not meet enrollment criteria is inadvertently enrolled, that participant must be discontinued from study and the Sponsor or Sponsor designee must be contacted. An exception may be granted in rare circumstances for which there is a compelling safety reason to allow the participant to continue and the Investigator needs to document.

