| 1. To assess the safety and reactogenicity of the study vaccines when given in co-administration or standalone | 
 • Local and systemic AEs reported within 7 days after each study vaccination • Unsolicited AEs reported within 28 days after each vaccination • SAE, AEs leading to early termination from study, MAAEs, and AESIs during the entire study period (6-month follow-up) | 
 • Proportion of participants with local and systemic solicited AEs; • Proportion of participants with unsolicited AEs; • Proportion of participants with SAEs; • Proportion of participants with MAAEs; • Proportion of participants with AESIs; • Proportion of participants with AEs leading to early termination from study; by Safety set. |

CONFIDENTIAL

Table 4 Objectives, Endpoints and Estimands

| Exploratory Immunogenicity Objectives | | |
|--|---|--|
| 1. To assess the immune response elicited by the ARCT-2303 vaccine against a panel of SARS-CoV-2 strains, as measured by VNA | SARS-CoV-2 neutralizing antibody responses with a panel of historical and new emergent SARS-CoV-2 strains on Days 1 and 29 in a subset of: 
• Standalone ARCT-2303 group recipients (Group 2a and/or 2b)• Standalone QIV group recipients (Group 3a and/or 3b) | 
• GMTs• GMFRs (post/pre-vaccination)• SCRs• Proportion of participants with antibody titer \geq LLOQ by PP set for immunogenicity. |
| 2. To assess the immunogenicity of influenza vaccine(s) when administered with or without ARCT-2303 as measured by microneutralization assay (in a subset of participants) | Microneutralization (MN) titers against influenza vaccine strains on Day 1 and Day 29, in: 
• Co-admin group recipients (a subset of participants from Group 1a and/or 1b)• Standalone QIV group recipients (a subset of participants from Group 3a and/or 3b). | 
• GMTs• GMFRs (post/pre-vaccination)• SCRs• Proportion of participants with antibody titer \geq LLOQ 
For each influenza vaccine strain, by PP set for immunogenicity.
 |

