5.3 Contraindications for the Second Vaccination

The following events constitute absolute contraindications to further administration of study vaccines.

If any of these events occur during the study, the participant must not receive additional doses of vaccine, but should be encouraged to continue study participation for safety at the discretion of the investigator:

- Anaphylaxis or systemic hypersensitivity reaction following the administration of vaccine.
- Any SAE judged to be related to study vaccination.
- Pregnancy.
- Any adverse event that, in the opinion of the investigator, poses an additional risk to the participant if he/she continues to participate in the study.

The following events constitute contraindications to administration of study vaccine at certain points in time, and if any of these events occur at the time scheduled for vaccination, the participant may be vaccinated at a later date, preferably within the time window specified in the protocol (Table 1), or the participant may be withdrawn at the discretion of the investigator:

- Any COVID-19 that occurred after Visit 1 or a positive result of COVID-19 test pre-vaccination.
- Acute moderate or severe infection with or without fever at the time of vaccination.
- Fever, defined as temperature $\geq 38.0^{\circ}\text{C}$ (100.4°F ; measured by any method) at the time of vaccination.

Participants with a minor illness without fever, as assessed by the investigator, can be administered study vaccines.

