5.5 Prohibited Medications

The use of an excluded medication/therapy is a protocol violation and must be recorded in the eCRF. The use of an excluded medication does not require the withdrawal of a participant from the study.

The following medications are prohibited:

- Receipt of any licensed or investigational COVID-19 vaccine during the study period;
- Receipt of any licensed or investigational influenza vaccine within 6 months prior to Day 1 or during the study period;
- Receipt of any licensed vaccines within 14 days prior to Day 1 or up to 14 days after the second study vaccination;
- Receipt of any investigational product within 28 days prior to Day 1 (or 5 half-lives of the investigational product, if longer) or during the study period;
- Immunomodulatory, immunostimulatory, or immunosuppressive therapy, including interferon and cytotoxic agents, within 90 days prior to Day 1 or during the study period;
- Systemic corticosteroids exceeding 10 mg/day of prednisone equivalent for ≥ 10 days within 30 days prior to Day 1 or during the study period;
- Intravenous immunoglobulins and/or any blood products within 3 months prior to Day 1 or during the study period.

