9.1.13 Pregnancy

Female participants of childbearing potential are to have a urine or blood pregnancy test (at investigator discretion or per local requirements) prior to the study vaccine administration. The study vaccine may only be administered if the pregnancy test is negative.

Note: Pregnancy tests must be performed even if the participant is menstruating at the time of the study visit. Any female participant who becomes pregnant while participating in the study will discontinue the study vaccine. The participant will be encouraged to remain in the study for safety follow-up until the end of the study.

Details of pregnancies in female participants, for which the date of conception is within the entire study period, should be followed for pregnancy outcomes. Information on delivery and newborn should be reported to the Sponsor within 1 month of the end of the pregnancy. Information about newborn health condition may be collected at 6 or 12 months after birth.

Details of pregnancies in female partners of male participants will be collected according to local regulations.

If a pregnancy is reported, the investigator should inform the Sponsor within 24 hours of learning of the pregnancy and should follow the procedures outlined in [Appendix 1](#).

Abnormal pregnancy outcomes (e.g., spontaneous abortion, fetal death, stillbirth, congenital anomalies, ectopic pregnancy) are considered SAEs.

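### Protocol 7.1 by default removes ineligible participants from the study even after dosing, which conflicts with 5.5 and stops scheduled collection of new safety events

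*Protocol*

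**What the plan says.** The rule is in the last paragraph of Protocol 7.1, a section about discontinuing study treatment: "If a participant who does not meet enrollment criteria is inadvertently enrolled, that participant must be discontinued from study". The next sentence softens it: "An exception may be granted in rare circumstances for which there is a compelling safety reason to allow the participant to continue". The investigator must document the exception. The section does not say who grants it or what would qualify.

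Other parts of the protocol treat related situations differently:

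- The opening of 7.1: "A participant withdrawn from the study vaccine may continue further study procedures (safety or immunogenicity) if planned in the study protocol".
- 5.3, after an absolute contraindication to further doses: the participant "should be encouraged to continue study participation for safety at the discretion of the investigator".
- 9.1.13, after pregnancy: "The participant will be encouraged to remain in the study for safety follow-up until the end of the study".
- 5.5, on prohibited medications and vaccines: "The use of an excluded medication does not require the withdrawal of a participant from the study".

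The secondary safety objective (Protocol Table 4) counts SAEs, MAAEs, AESIs and AEs leading to early termination over the whole 6 months.

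**The concern.** An eligibility error may come to light only after the Day 1 injections. Some exclusion criteria exist because the protocol judges vaccination too risky for the person, for example previous myocarditis (exclusion 7) or Guillain-Barré syndrome (exclusion 8). Read literally, 7.1 sends such a vaccinated person out of the study unless the rare exception is granted. The trial then stops looking for new events in someone it has exposed and considers to be at higher risk.

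Two things are at stake. The main one is observation of those participants. The other is the 6-month safety proportions, which lose observation time in a group selected partly on risk. A site also faces conflicting instructions where the breach is one that 5.5 covers.

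**Working it through.** The plan gives no figure on this point, so there is none to reproduce. The check is mainly a comparison of texts, with a small sizing at the end.

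**1. Protocol 7.1 against 5.5.** Section 5.5 has seven items. The first (COVID-19 vaccine during the study) has no pre-Day 1 window. The other six do, and each matches an exclusion criterion in 5.2:

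| 5.5 item, pre-Day 1 window | Exclusion criterion |
|---|---|
| Influenza vaccine, 6 months | 19 |
| Other licensed vaccine, 14 days | 20 |
| Investigational product, 28 days or 5 half-lives | 17 |
| Immunomodulatory or immunosuppressive therapy, 90 days | 11 |
| Systemic corticosteroids above the stated limit, 30 days | 12 |
| Immunoglobulins or blood products, 3 months | 13 |

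Take a participant found after Day 1 to have had an influenza vaccine four weeks before enrolment. Under 5.5 this does not require withdrawal. Under 7.1 the person is ineligible and must leave. Both rules apply to the same fact, so this is a direct conflict.

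**2. Protocol 7.1 against its own opening, 5.3 and 9.1.13.** These cover withdrawal from vaccine, or events arising after enrolment. None gives an instruction for a person who should not have been enrolled. They do not contradict the rule, but they follow a different principle: injections stop, observation may or should continue.

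**3. What remains and what stops after removal.**

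- Remaining: an early termination visit where possible (8.12.6), follow-up of events already reported (9.1.10), follow-up of myocarditis or pericarditis cases to resolution (9.1.14.1), and notification of a later SAE if the investigator learns of it and judges it related (9.1.10).
- Stopping: collection of new SAEs, MAAEs and AESIs, which under 9.1.7 runs only to the participant's last study procedure. Under 9.1.10 the investigator has no duty to look for events in former participants.
- Section 9.1.14.1 asks participants to report cardiac symptoms for 6 weeks (42 days) after each vaccination. Removal on Day 10 or Day 29 is 9 or 28 days after the first injection, so inside that window.

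**4. Effect on the endpoint.** The Safety Set takes every exposed participant with any evaluable post-vaccination safety data (Protocol Table 8; SAP 4.1.5), so the removed person normally stays in the denominator. The analyses are proportions of participants with an event, cumulative to end of study (SAP 7.2), and missing results are not imputed (SAP 3.5). An unobserved event counts as no event, so the error runs downward.

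**5. Size.** Day 1 to Day 181 is 180 days.

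- Error found on Day 10: (181 − 10)/180 = 171/180 = 95% of scheduled observation lost.
- Error found on Day 29: (181 − 29)/180 = 152/180 = 84% lost.
- Number affected: not in the documents. Assuming 1% to 3% of 1680: 0.01 × 1680 = 16.8 and 0.03 × 1680 = 50.4, so about 17 to 50 people.

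Let f be the fraction removed, L the share of observation lost, and r the event risk of removed participants relative to the rest. If risk is roughly proportional to observed time, the relative shortfall in the 6-month proportion is f × r × L / (1 − f + f × r). With r = 1 this is f × L:

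- low end: 0.01 × 0.84 = 0.0084, about 0.8% of the true proportion;
- high end: 0.03 × 0.95 = 0.0285, about 2.9% of the true proportion.

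The shortfall grows with r, nearly in proportion while f is small. The documents give no value for r.

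**The case against.** The case for leaving the rule alone has several sound parts.

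- A reader might infer that anyone found ineligible must leave. The text does not support that: the exception turns on a safety reason and could cover a discovered history of myocarditis. It is, however, rare by its own terms, without criteria, and leaves removal as the default.
- A reader might infer that safety follow-up ends. It is curtailed, not ended, as step 3 shows, so the 95% and 84% losses refer to scheduled collection of new events and are worst cases.
- A reader might say that every other section separates dosing from participation. That goes too far. Section 7.2 lets the investigator withdraw a participant from the study for safety, compliance or administrative reasons, 5.3 allows withdrawal for temporary contraindications, and its encouragement to stay is itself discretionary. The only direct conflict is with 5.5, which concerns medications and vaccines, not the medical-history exclusions that matter most for safety.
- A reader might infer a biased comparison between groups. Nothing shows that. The rule is the same in every randomized group, and safety is descriptive without testing. Many eligibility breaches, such as being site staff, also carry no personal risk.
- A reader might assume that keeping these participants cannot touch the coprimary analyses. That is not established. SAP 4.1.4 lists forbidden conditions and prohibited medications or vaccines as reasons for PP exclusion, but has no general item for eligibility breaches; too few previous COVID-19 vaccine doses, for instance, is not listed. Protocol 10.3 also names mITT for the primary objectives, and someone kept to Day 29 with a result would enter it.

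What survives is the default itself, its conflict with 5.5, and the loss of scheduled observation in people already dosed.

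**Conclusion.** The point holds as a default rule that is poorly aligned with the rest of the protocol, not as a general loss of follow-up. The conflict between 7.1 and 5.5 follows from the text and needs no assumption. So does the end of scheduled collection of new events for a dosed participant removed under 7.1.

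The numerical effect on the 6-month proportions is probably small: about 0.8% to 2.9% in relative terms if 1% to 3% of participants are removed between Day 10 and Day 29 with average risk, and more if their risk is higher. That range assumes no use of the exception and no later spontaneous reports. The true number affected is unknown. The stronger reason to act is that some vaccinated participants at higher risk would no longer be actively observed.

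**What to change.** The sponsor should reconcile Protocol 7.1 with 5.5, 5.3 and 9.1.13. For a participant who has received any study injection, an eligibility error should not by default end the safety contacts and AE collection already scheduled to Day 181, subject to consent and to the withdrawal provisions of 7.2.

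Whether such a participant may receive a further injection is for the sponsor's reconciled rule. The amendment should state it explicitly, because 5.3 has no item for an eligibility breach as such. Simply deleting the sentence in 7.1 could leave the question open.

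The SAP should say how these participants' immunogenicity data are treated: whether an eligibility breach not listed in 4.1.4 leads to PP exclusion, and whether the participant counts in mITT.

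The cost is a short protocol amendment, a clarification in the SAP, and contacts already planned for each participant. No new visits are needed.

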7.2 Participant Withdrawal from the Study

A participant may withdraw from the study at any time at his/her own request, or may be withdrawn, at any time at the discretion of the investigator for safety, behavioral, compliance, or administrative reasons.

If the participant withdraws consent for disclosure of future information, the Sponsor may retain and continue to use any data collected before such a withdrawal of consent.

If a participant withdraws from the study, he/she may request destruction of any samples taken and not tested, and the investigator must document this in the study center study records and inform the Sponsor’s representative.

See the SoA ([Table 1](#)) for data to be collected at the time of study discontinuation and follow-up and for any further evaluations that need to be completed.

Primary reason relative to premature discontinuation from the study will be documented in the eCRF:

- AE(s).

CONFIDENTIAL

- Participant decision, not due to an AE.
- If a female participant becomes pregnant (such participants will be followed up as described in [Section 9.1.13](#) and [Appendix 1](#)).
- Lost to follow-up.
- Sponsor study termination.
- Other (specify).

7.3 Lost to Follow-up

A participant will be considered lost to follow-up if he or she repeatedly fails to return for scheduled visits and is unable to be contacted by the study center.

If a participant fails to return to the clinic for a required study visit, the study site must attempt to contact the participant and reschedule the missed visit as soon as possible and counsel the participant on the importance of maintaining the assigned visit schedule and ascertain whether or not the participant wishes to and/or should continue in the study.

Before a participant is deemed lost to follow-up, the investigator or designee must make every effort to regain contact with the participant (where possible, 3 telephone calls and, if necessary, a certified letter to the participant's last known mailing address or local equivalent methods). These contact attempts should be documented in the participant's medical record.

Should the participant continue to be unreachable, he/she will be considered to have withdrawn from the study.

CONFIDENTIAL

May not be used, divulged, published or otherwise disclosed without written consent of Arcturus Therapeutics, Inc.

